8.2.3. Demographics/Medical History

Demographic information relating to the participant's sex, age, and race will be recorded at Screening on the appropriate eCRF page.

Additionally, information regarding participant occupational circumstances (eg, essential worker status) will be collected at Screening.

Medical history of each participant, including risk factors for severe COVID-19 as defined in [Section 6.2.1.1](#), will be collected and recorded on the Medical History eCRF page. Significant findings that were present prior to the signature of the informed consent will also be included in the Medical History eCRF page.

Study participants will also be asked to report history of receipt of seasonal influenza vaccine during the current influenza season (typically October through April in the Northern Hemisphere) as a concomitant medication.

8.2.4. Physical Examination

A full physical examination, including vital signs, height, and weight, will be performed at Screening and on Day 1, and symptom-directed physical examinations at other scheduled timepoints as indicated in the SoEs ([Section 11.1](#)). The full examination will include assessment of skin, head, ears, eyes, nose, throat, neck, thyroid, lungs, heart, cardiovascular, abdomen, lymph nodes, and musculoskeletal system/extremities. Symptom-directed physical examinations may be performed at other timepoints at the discretion of the investigator.

On each dosing day before injection, the arm receiving the injection should be examined and the associated lymph nodes should be evaluated.

Body mass index will be calculated at the Screening Visit (Day 0).

Any clinically significant finding identified during a study visit after the first dose should be reported as an MAAE.

Significant new findings that begin or worsen after informed consent must be recorded on the AE eCRF page.

8.2.5. Vital Sign Measurements

Vital signs will be measured at the timepoints indicated in the SoEs ([Section 11.1](#)). The participant will be seated for at least 5 minutes before all measurements are taken. On Day 1 and Day 29, vital sign measurements will be collected once before IP injection and at least 30 minutes after IP injection (before participants are discharged from the study site). When applicable, vital sign measurements should be performed before blood collection.

Febrile participants at Day 1 and Day 29 visits (fever is defined as a body temperature $\geq 38.0^{\circ}\text{C}/100.4^{\circ}\text{F}$) may be rescheduled within the relevant window periods. Criteria for delay of study treatment are provided in [Section 7.1](#). Afebrile participants with minor illnesses may be injected at the discretion of the investigator.

If any of the vital sign measurements meet the toxicity grading criteria for clinical abnormalities of Grade 3 or greater, the abnormal value and grade will be documented on the AE page of the eCRF (unless there is another known cause of the abnormality that would result in an AE classification). The investigator will continue to monitor the participant with additional assessments until the vital sign value has reached the reference range, returns to the vital sign value at baseline, is considered stable, or until the investigator determines that follow-up is no longer medically necessary.

8.2.6. Blood Sampling

The maximum planned volumes of blood sampled for immunogenicity analyses per participant are approximately 50 mL for 1 day, 100 mL for 28 days ([Table 16](#)), and 300 to 420 mL (dependent on participation in Part B and Part C) for the total study volume ([Table 4](#)).

Table 4: Maximum Planned Immunogenicity Blood Sampling Volumes per Participant by Visit

Study Visit Day	Table 16 D1	Table 16 D29	Table 16 D57	Table 17 D209	Table 17 D394	Table 18 D759	Total
Immunogenicity blood samples ^a	50 mL	50 mL	50 mL	50 mL	50 mL	50 mL	300 mL
Study Visit Day	Part B Day 1^b	Part B Day 29^b	Part B Day 57^b	NA	NA	NA	NA
Immunogenicity blood samples ^a	20 mL	20 mL	20 mL	NA	NA	NA	60 mL ^c
Study Visit Day	Part C Day 1^d	Part C Day 4^d	Part C Day 29^d	Part C Day 181^d	NA	NA	NA
Immunogenicity blood samples ^a	24 mL	8 mL	24 mL	24 mL	NA	NA	80 mL

Abbreviations: COVID-19 = coronavirus disease 2019; D = Day; NA = not applicable; RT-PCR = reverse transcriptase polymerase chain reaction; OL = open-label; SoE = schedule of events.

^a Additional blood samples (16 mL) will be taken at Illness Day 1 and Convalescent Visit Day 28 for those participants who report symptoms of COVID-19 and who have RT-PCR confirmed symptomatic COVID-19, respectively.

^b If a visit from SoE [Table 16](#) and [Table 17](#) and a Part B visit overlap, only the Part B sample will be taken (using the Part B kit). The exception would be if an Illness Day 1 or Convalescent Visit Day 28 overlapped with a Part B visit. In this case the Illness and Convalescent Visit Day 28 samples would be taken and the corresponding kits used.

- ^c For participants who received placebo during the Part A Blinded Phase and receive mRNA-1273 during Part B. Note that immunogenicity blood samples are collected only on OL-D1 and OL-D57 (Table 21) or OL-D1 and OL-D29 (Table 22) in Part B.
- ^d If a visit from SoE Table 17 and Table 18 and a Part C visit overlap, only the Part C sample will be taken (using the Part C kit). Exceptions would be if an Illness Day 1 or Convalescent Visit Day 28 overlapped with a Part C visit, in this case the Illness and Convalescent Visit Day 28 samples would be taken and corresponding kits used, or in the case of a Part C Day 4 visit, both sets of samples would need to be taken using both kits.

8.3. Safety Definitions and Procedures

8.3.1. Adverse Event

An AE is defined as any untoward medical occurrence associated with the use of a drug in humans, whether or not considered drug related.

A treatment-emergent AE (TEAE) is defined as any event not present before exposure to IP or any event already present that worsens in intensity or frequency after exposure.

Events Meeting the Adverse Event Definition

- Exacerbation of a chronic or intermittent pre-existing condition including either an increase in frequency and/or intensity of the condition.
- New conditions detected or diagnosed after the first dose of IP even though they may have been present before the start of the study.

Events NOT Meeting the Adverse Event Definition

- Medical or surgical procedure (eg, endoscopy, appendectomy): the condition that leads to the procedure should be the AE.
- Situations in which an untoward medical occurrence did not occur (social and/or convenience admission to a hospital).

An AR is any AE for which there is a reasonable possibility that the IP caused the AE (Section 8.3.5). For the purposes of investigational new drug safety reporting, “reasonable possibility” means that there is evidence to suggest a causal relationship between the IP and the AE.

An unsolicited AE is any AE reported by the participant that is not specified as a solicited AR in the protocol; or is specified as a solicited AR in the protocol, but starts outside the protocol-defined period for reporting solicited ARs (ie, for the 7 days after each dose of IP, Part A, Blinded Phase only).

8.3.2. Medically Attended Adverse Events

An MAAE is an AE that leads to an unscheduled visit (including a telemedicine visit) to a healthcare practitioner (HCP). This would include visits to a study site for unscheduled

assessments (eg, rash assessment, abnormal laboratory follow-up, COVID-19 [Section 8.1.1]) and visits to HCPs external to the study site (eg, urgent care, primary care physician). Investigators will review unsolicited AEs for the occurrence of any MAAEs. All MAAEs must be fully reported on the MAAE page of the eCRF.

8.3.2.1. Anaphylaxis

All suspected cases of anaphylaxis should be recorded as MAAEs and reported as an SAE, based on criteria for a medically important event, unless the event meets other serious criteria. As an SAE, the event should be reported to the Sponsor or designee immediately and in all circumstances within 24 hours as per Section 8.3.12 (Reporting SAEs). The investigator will submit any updated anaphylaxis case data to the Sponsor within 24 hours of it being available. For reporting purposes, a participant who displays signs/symptoms consistent with anaphylaxis as shown below should be reported as a potential case of anaphylaxis. This is provided as general guidance for investigators and is based on the Brighton Collaboration case definition (Rüggeberg et al 2007).

Anaphylaxis is an acute hypersensitivity reaction with multi-organ system involvement that can present as, or rapidly progress to, a severe life-threatening reaction. It may occur following exposure to allergens from a variety of sources. Anaphylaxis is a clinical syndrome characterized by:

- Sudden onset AND
- Rapid progression of signs and symptoms AND
- Involving 2 or more organ systems, as follows:
 - **Skin/mucosal:** urticaria (hives), generalized erythema, angioedema, generalized pruritus with skin rash, generalized prickle sensation, red and itchy eyes
 - **Cardiovascular:** measured hypotension, clinical diagnosis of uncompensated shock, loss of consciousness or decreased level of consciousness, evidence of reduced peripheral circulation
 - **Respiratory:** bilateral wheeze (bronchospasm), difficulty breathing, stridor, upper airway swelling (lip, tongue, throat, uvula, or larynx), respiratory distress, persistent dry cough, hoarse voice, sensation of throat closure, sneezing, rhinorrhea
 - **Gastrointestinal:** diarrhea, abdominal pain, nausea, vomiting

8.3.3. Adverse Events of Special Interest

An AESI is a serious or nonserious AE of scientific and medical concern specific to the Sponsor's product or program, for which ongoing monitoring and immediate notification by the investigator to the Sponsor is required and documentation is in the form of a case narrative. Such events may

require further investigation to characterize and understand them. Refer to [Section 11.5](#) for a list of AESIs pertinent to this study. All AESIs will be collected for participants receiving the BD in Part C through the remaining study period and must be reported to the Sponsor or designee immediately and in all circumstances within 24 hours of becoming aware of the event via the electronic data capture system. If a site receives a report of a new AESI from a study participant or receives updated data on a previously reported AESI, and the eCRF has been taken offline, then the site can report this information on a paper AESI form using the SAE Mailbox, the SAE Hotline, or the SAE Fax line ([Section 8.3.11](#)).

Acute Myocarditis and/or Pericarditis

These definitions are intended to serve as a guide to help in the reporting of suspected cases of myocarditis and/or pericarditis; however, the diagnosis of suspected cases is left to the investigator's clinical judgement.

All suspected cases of probable and confirmed myocarditis, pericarditis, or myopericarditis should be recorded as an AESI, and reported as an SAE, if the event meets seriousness criteria. As an SAE, the event should be reported to the Sponsor or designee immediately and in all circumstances within 24 hours as per [Section 8.3.11](#). The investigator will submit any updated myocarditis, pericarditis, or myopericarditis case data to the Sponsor within 24 hours of it being available. For reporting purposes, a participant who displays signs/symptoms consistent with the CDC case definitions as described below ([Gargano et al 2021](#)), should be reported as a potential case of confirmed or probable myocarditis, pericarditis, or myopericarditis.

Acute Myocarditis Case Definition

Presence of ≥ 1 new or worsening of the following clinical symptoms (persons who lack the listed symptoms but who meet other criteria may be classified as subclinical myocarditis [probable or confirmed]):

- Chest pain/pressure/discomfort
- Dyspnea/shortness of breath/pain with breathing
- Palpitations
- Syncope

AND

For PROBABLE CASE:

Presence of ≥ 1 new finding of the following:

- Troponin level above upper limit of normal (any type of troponin)

- Abnormal electrocardiogram (ECG or EKG) or rhythm monitoring findings consistent with myocarditis
 - To meet the ECG or rhythm monitoring criterion, a probable case must include at least 1 of the following:
 - ST segment or T-wave abnormalities
 - Paroxysmal or sustained atrial, supraventricular, or ventricular arrhythmias
 - AV nodal conduction delays or intraventricular conduction defects
- Abnormal cardiac function or wall motion abnormalities on echocardiogram
- Cardiac magnetic resonance imaging (cMRI) finding consistent with myocarditis ([Ferreira et al 2018](#))

AND

- No other identifiable cause of the symptoms and findings

For CONFIRMED CASE:

- Histopathologic confirmation of myocarditis (using Dallas criteria [[Aretz et al 1987](#)])

OR

- cMRI findings consistent with myocarditis in the presence of troponin level above upper limit of normal (any type of troponin)

AND

- No other identifiable cause of the symptoms and findings

Acute Pericarditis Case Definition

Presence of ≥ 2 new or worsening of the following clinical features ([Adler et al 2015](#)):

- Acute chest pain (Typically described as pain made worse by lying down, deep inspiration, or cough; and relieved by sitting up or leaning forward, although other types of chest pain may occur)
- Pericardial rub on examination
- New ST-elevation or PR-depression on EKG
- New or worsening pericardial effusion on echocardiogram or magnetic resonance imaging

Myopericarditis Case Definition

Participants who meet criteria for both myocarditis and pericarditis may be described under myopericarditis.

8.3.4. Serious Adverse Events

An AE (including an AR) is considered an SAE if, in the view of either the investigator or Sponsor, it results in any of the following outcomes:

- **Death**

A death that occurs during the study or that comes to the attention of the investigator during the protocol-defined follow-up period must be reported to the Sponsor, whether or not it is considered related to IP.

- **Is life-threatening**

An AE is considered life-threatening if, in the view of either the investigator or the Sponsor, its occurrence places the participant at immediate risk of death. It does not include an AE that, had it occurred in a more severe form, might have caused death.

- **Inpatient hospitalization or prolongation of existing hospitalization**

In general, inpatient hospitalization indicates the participant was admitted to the hospital or emergency ward for at least one overnight stay for observation and/or treatment that would not have been appropriate in the physician's office or outpatient setting. The hospital or emergency ward admission should be considered an SAE regardless of whether opinions differ as to the necessity of the admission. Complications that occur during inpatient hospitalization will be recorded as an AE; however, if a complication/AE prolongs hospitalization or otherwise fulfills SAE criteria, the complication/AE will be recorded as a separate SAE.

- **Persistent or significant incapacity or substantial disruption of the ability to conduct normal life functions**

This definition is not intended to include experiences of relatively minor medical significance such as uncomplicated headache, nausea/vomiting, diarrhea, influenza, and accidental trauma (eg, sprained ankle) which may interfere with or prevent everyday life functions but do not constitute a substantial disruption.

- **Congenital anomaly or birth defect**

- **Medically important event**

Medical judgment should be exercised in deciding whether SAE reporting is appropriate in other situations, such as important medical events that may not be immediately life-threatening or result in death or hospitalization but may jeopardize the participant or require medical or surgical intervention to prevent one of the other outcomes listed in the

above definition. These events should usually be considered serious. Examples of such medical events include allergic bronchospasm requiring intensive treatment in an emergency room or at home, blood dyscrasias or convulsions that do not result in inpatient hospitalization, or the development of drug dependency or drug abuse.

8.3.5. Solicited Adverse Reactions (Part A)

The term “reactogenicity” refers to the occurrence and intensity of selected signs and symptoms (ARs) occurring after IP injection. The eDiary will solicit daily participant reporting of ARs using a structured checklist ([Section 8.2.2](#)). Participants will record such occurrences in an eDiary on the day of IP injection and for the 6 days after the day of dosing.

Severity grading of reactogenicity will occur automatically based on participant entry into the eDiary according to the grading scales presented in [Table 5](#) modified from the Toxicity Grading Scale for Healthy Adult and Adolescent Volunteers Enrolled in Preventative Vaccine Clinical Trials ([DHHS 2007](#)).

If a solicited local or systemic AR continues beyond 7 days after dosing, the participant will be prompted daily to capture solicited local or systemic AR in the eDiary until resolution. Adverse reactions recorded in eDiaries beyond Day 7 should be reviewed by the investigator either via phone call or at the following study visit. All solicited ARs (local and systemic) will be considered causally related to dosing.

Table 5: Solicited Adverse Reactions and Grades

Reaction	Grade 0	Grade 1	Grade 2	Grade 3	Grade 4
Injection site pain	None	Does not interfere with activity	Repeated use of over-the-counter pain reliever > 24 hours or interferes with activity	Any use of prescription pain reliever or prevents daily activity	Requires emergency room visit or hospitalization
Injection site erythema (redness)	< 25 mm/ < 2.5 cm	25 – 50 mm/ 2.5 – 5 cm	51 – 100 mm/ 5.1 – 10 cm	> 100 mm/ > 10 cm	Necrosis or exfoliative dermatitis
Injection site swelling/induration (hardness)	< 25 mm/ < 2.5 cm	25 – 50 mm/ 2.5 – 5 cm	51 – 100 mm/ 5.1 – 10 cm	> 100 mm/ > 10 cm	Necrosis
Axillary (underarm) swelling or tenderness ipsilateral to the side of injection	None	No interference with activity	Repeated use of over-the-counter (non-narcotic) pain reliever > 24 hours or some interference with activity	Any use of prescription (narcotic) pain reliever or prevents daily activity	Emergency room visit or hospitalization
Headache	None	No interference with activity	Repeated use of over-the-counter pain reliever > 24 hours or some interference with activity	Significant; any use of prescription pain reliever or prevents daily activity	Requires emergency room visit or hospitalization
Fatigue	None	No interference with activity	Some interference with activity	Significant; prevents daily activity	Requires emergency room visit or hospitalization
Myalgia (muscle aches all over body)	None	No interference with activity	Some interference with activity	Significant; prevents daily activity	Requires emergency room visit or hospitalization
Arthralgia (joint aches in several joints)	None	No interference with activity	Some interference with activity	Significant; prevents daily activity	Requires emergency room visit or hospitalization

Reaction	Grade 0	Grade 1	Grade 2	Grade 3	Grade 4
Nausea/vomiting	None	No interference with activity or 1-2 episodes/24 hours	Some interference with activity or > 2 episodes/24 hours	Prevents daily activity, requires outpatient intravenous hydration	Requires emergency room visit or hospitalization for hypotensive shock
Chills	None	No interference with activity	Some interference with activity not requiring medical intervention	Prevents daily activity and requires medical intervention	Requires emergency room visit or hospitalization
Fever (oral)	< 38.0°C < 100.4°F	38.0 – 38.4°C 100.4 – 101.1°F	38.5 – 38.9°C 101.2 – 102.0°F	39.0 – 40.0°C 102.1 – 104.0°F	> 40.0°C > 104.0°F

Any solicited AR that meets any of the following criteria must be entered into the participant's source document and must also be recorded as an AE in the participant's Adverse Event eCRF:

- Solicited local or systemic AR that results in a visit to an HCP (MAAE)
- Solicited local or systemic AR leading to the participant withdrawing from the study or the participant being withdrawn from the study by the investigator (AE leading to withdrawal)
- Solicited local or systemic AR lasting beyond 7 days post injection
- Solicited local or systemic AR that leads to participant withdrawal from IP
- Solicited local or systemic AR that otherwise meets the definition of an SAE

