3. OBJECTIVES AND ENDPOINTS

Table 1: Objectives and Endpoints

Objectives and Endpoints	
Primary Objective	Primary Endpoints

Efficacy Objective (Primary): To demonstrate the efficacy of mRNA-1273 to prevent COVID-19.
	
Efficacy Endpoints (Primary): Vaccine efficacy of mRNA-1273 to prevent the first occurrence of COVID-19 starting 14 days after the second dose of IP, where COVID-19 is defined as symptomatic disease based on the following criteria:
 
 • The participant must have experienced at least TWO of the following systemic symptoms: fever ($\geq 38^{\circ}\text{C}$), chills, myalgia, headache, sore throat, new olfactory and taste disorder(s), OR • The participant must have experienced at least ONE of the following respiratory signs/symptoms: cough, shortness of breath or difficulty breathing, OR clinical or radiographical evidence of pneumonia; AND • The participant must have at least 1 NP swab or saliva sample (or respiratory sample, if hospitalized) positive for SARS-CoV-2 by RT-PCR

Safety Objective (Primary): To evaluate the safety and reactogenicity of 2 injections of the mRNA-1273 vaccine given 28 days apart.
	
Safety Endpoint (Primary):
 
 • Solicited local and systemic ARs through 7 days after each dose of IP (Part A). • Unsolicited AEs through 28 days after each dose of IP (Part A [all participants] and Part C [only those who receive the BD]). • MAAEs or AEs leading to withdrawal through the entire study period. • SAEs throughout the entire study period.

Objectives and Endpoints	
Efficacy Objectives (Secondary)	Efficacy Endpoints (Secondary)

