9.5.2.1. Adverse Events

Safety and reactogenicity will be assessed by clinical review of all relevant parameters. Safety analyses will be provided for Parts A, B, and C separately unless specified otherwise.

The number and percentage of participants with any solicited local AR, with any solicited systemic AR, and with any solicited AR during the 7-day follow-up period after each dose will be provided only for Part A. A 2-sided 95% exact CI using the Clopper-Pearson method will be also provided for the percentage of participants with any solicited AR for each treatment group. Analysis of solicited AR will be provided using the Solicited Safety Set for Part A.

The number and percentage of participants with unsolicited AEs (Part A [all participants] and Part C [only those who receive the BD]), SAEs, MAAEs, AESIs (Part C [only those who receive the BD]), and AEs leading to discontinuation from IP or withdrawal from the study will be summarized. Unsolicited AEs will be presented by MedDRA preferred term and system organ class. Analyses of AEs will be provided for Part A and Part B using the Safety Set. For Part C, analysis of AEs will be provided in the Part C Safety Set (ie, participants who received booster in Part C).

For all other safety parameters, descriptive summary statistics will be provided, and [Table 12](#) summarizes the analysis strategy for safety parameters. Further details will be described in the SAP.

Table 12: Analysis Strategy for Safety Parameters in Part A

Safety Endpoint	Number and Percentage of Participants, Number of Events	95% CI
Any Solicited AR (Part A; overall and by local, systemic)	X	X
Any Unsolicited AE	X	
Any SAE	X	
Any Unsolicited MAAE	X	
Any Unsolicited Treatment-Related AE	X	
Any Treatment-Related SAE	X	
Discontinuation due to AE	X	
Any Grade 3 and above AE	X	
Any Treatment-Related Grade 3 and above AE	X	

Abbreviations: AE = adverse event; AR = adverse reaction; CI = confidence interval; MAAE = medically attended adverse event; MedDRA = Medical Dictionary for Regulatory Activities; SAE = serious adverse event.

Notes: 95% CI using the Clopper-Pearson method, X = results will be provided. Unsolicited AEs will be summarized by System Organ Class and Preferred Term coded by MedDRA. Safety parameters will be analyzed in applicable study parts and participants as further specified in the statistical analysis plan.

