6.6.1.1. Overview of Unsolicited TEAEs

An overall summary of unsolicited TEAEs including the number and percentage of subjects by treatment group who experience the following will be presented:

- Any unsolicited TEAEs
- Any serious AEs
- Any unsolicited AEs that are medically-attended
- Any unsolicited TEAEs leading to discontinuation from participation in the study
- Any unsolicited severe TEAEs (severity of AEs is assessed as mild, moderate and severe)
- Any unsolicited TEAEs that are fatal

The table will also include number and percentage of subjects with unsolicited TEAEs that are treatment-related in each of the above categories.

The overall summary will be provided for unsolicited TEAE up to 28 days after any injection, and for the Overall Stage throughout Part A respectively.

In addition, separate listings containing individual subject adverse event data for unsolicited TEAEs leading to discontinuation from study vaccine, unsolicited TEAEs leading to discontinuation from participation in the study, serious AEs, serious treatment-related AEs, and unsolicited treatment-related medically-attended AEs may be provided. Listing of deaths including cause of death, and listing of TEAEs in subjects who died will be provided.

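### Non-serious solicited reactions that lead to a healthcare visit are MAAEs under protocol 8.3.5, but every explicit MAAE row counts only unsolicited AEs, so the rows undercount the endpoint and the Primary Series cohorts are not counted alike

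*Protocol*

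**What the plan says.** **Endpoint.** Protocol Table 1 (Section 3) lists "MAAEs or AEs leading to withdrawal through the entire study period" as a primary safety endpoint. SAP Part A 3.1.2 and SAP Part B/C 3.1.2 repeat it. None of the three limits it to unsolicited events.

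**Recording rule.** Protocol 8.3.5 lists the solicited reactions that must also go on the Adverse Event eCRF. The first is "Solicited local or systemic AR that results in a visit to an HCP (MAAE". A solicited reaction that causes study withdrawal is listed too and labelled an AE leading to withdrawal.

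**Definition.** Protocol 8.3.1 states: "An unsolicited AE is any AE reported by the participant that is not specified as a solicited AR in the protocol". A solicited term becomes unsolicited only if it starts outside the solicitation period, which is 7 days after each dose and applies to Part A only.

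**Analysis rows.** Protocol Table 12 (9.5.2.1) has the row "Any Unsolicited MAAE". The overview in SAP Part A 6.6.1.1 has "Any unsolicited AEs that are medically-attended" and "Any unsolicited TEAEs leading to discontinuation from participation in the study". The system organ class and preferred term list in 6.6.1.2 carries the same limits, as do SAP Part B/C 5.4.1.1 and 5.4.1.2. The SAE rows in the same lists carry no such limit.

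**The concern.** A participant who takes a day-2 fever or a painful arm to urgent care after a Part A dose has an MAAE by 8.3.5 but not an unsolicited AE by 8.3.1. If the event is not serious, it meets none of the explicit MAAE rows.

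Two things are at stake:

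- **The Part A comparison.** Protocol 2.3.3 says saline recipients may be at lower risk of injection-related AEs, so the omitted events are expected to fall more on vaccine. The overview also repeats each category for treatment-related events. Protocol 8.3.5 treats every solicited reaction as related, so the treatment-related MAAE row leaves out events that are related by rule.
- **The Primary Series tables.** SAP Part B/C sets the mRNA-1273 cohort (dosed in Part A) beside the Placebo-mRNA-1273 cohort (dosed in Part B). Part B collects no solicited reactions, so the same fever and clinic visit is an unsolicited MAAE in the second cohort and not in the first.

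**Working it through.** The documents state no MAAE rate, so there is no figure to reproduce. The check is of the text, followed by an illustration on assumed rates.

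**Text, step by step**

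1. The endpoint is all MAAEs (Table 1; SAP Part A 3.1.2).
2. A solicited reaction with an HCP visit is an MAAE and goes on the AE page (8.3.5).
3. If it starts within 7 days of a Part A dose, it is not unsolicited (8.3.1).
4. The explicit MAAE rows require unsolicited events (Table 12; SAP Part A 6.6.1.1, 6.6.1.2; SAP Part B/C 5.4.1.1, 5.4.1.2).
5. So a non-serious event satisfying steps 2 and 3 is in the endpoint but not in those rows. A serious one is still counted in the SAE rows.
6. In Part B the 7-day carve-out does not apply, so step 3 fails and the event is counted.

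**Illustration for Part A (all rates assumed)**

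Take n = 15,000 per arm (protocol Table 2) and an unsolicited MAAE rate b that is equal in both arms, so the unsolicited-only ratio is 1.00. Add reaction-driven MAAE rates v (vaccine) and p (placebo) without overlap.

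RR = (b + v)/(b + p), with a log-Wald 95% CI using SE = √[(1−P₁)/(nP₁) + (1−P₀)/(nP₀)], where P₁ = b + v and P₀ = b + p.

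Example: b = 5%, v = 0.2%, p = 0.05%. Participants omitted are 15,000 × 0.002 = 30 and 15,000 × 0.0005 = 7.5. RR = 5.20/5.05 = 1.030.

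| v / p | Omitted, vaccine / placebo | RR at b = 5% (95% CI) | RR at b = 10% (95% CI) |
|---|---|---|---|
| 0.05% / 0.01% | 7.5 / 1.5 | 1.008 (0.914–1.112) | 1.004 (0.938–1.074) |
| 0.2% / 0.05% | 30 / 7.5 | 1.030 (0.934–1.135) | 1.015 (0.949–1.086) |
| 1.0% / 0.2% | 150 / 30 | 1.154 (1.051–1.267) | 1.078 (1.010–1.152) |

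**Treatment-related row (assumed).** If related unsolicited MAAEs were 1.0% on vaccine and a further 0.2% were omitted, the row would show 1.0/1.2 of the true value, an understatement of one sixth.

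**Primary Series (assumed).** Suppose both cohorts had the same b and the same reaction-driven rate r. The Part A cohort would show b and the crossover cohort b + r. With b = 5% and r from 0.05% to 1.0%, that is 5.00% against 5.05% to 6.00%, a difference produced by the definition alone. Equal b is a simplification, because follow-up and calendar time differ between the cohorts.

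**The case against.** The strongest reply is that little is lost.

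- **Endpoint coverage.** A reader might infer that these events disappear from the primary safety endpoint altogether. The documents do not establish that. The 9.5.2.1 text lists MAAEs and AEs leading to withdrawal without the qualifier. The Overall Stage sentence in SAP Part A 6.6.1.2 names MAAEs plainly. But that sentence sits under a heading confined to unsolicited events, and the Overall Stage overview in 6.6.1.1 is restricted, so it is ambiguous.
- **Withdrawals.** A reader might infer that reaction-driven withdrawals are hidden. Table 12 has an unrestricted row for discontinuation due to AEs, and SAP Part A 6.2.1 tabulates study discontinuation by reason. This half of the point is weak.
- **Collection.** Protocol 8.3.2 says "Investigators will review unsolicited AEs for the occurrence of any MAAEs", which might be read as limiting the search to those events. It does not say only, and 8.3.5 captures the solicited ones separately. There is no data gap.
- **Reactions are tabulated anyway.** SAP Part A 6.6.2 gives every solicited reaction by arm and grade, and for most terms Grade 4 means an emergency room visit or hospitalization. This stands, but a visit for a lower-grade reaction is not identifiable as such in those tables.
- **Programming practice.** One could treat every AE-page record as unsolicited. That contradicts 8.3.1 and would put solicited reactions into the all-unsolicited-TEAE row. Either reading needs a written rule.
- **No biased ratio is printed.** SAP Part A 6.6.1 provides descriptive ratios by preferred term, not for the any-MAAE row. The ratios above illustrate the underlying contrast; they are not planned outputs.

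**Conclusion.** The mismatch is real and follows from the text. Following the explicit rows undercounts non-serious reaction-driven MAAEs after Part A doses, including in the treatment-related row, and it makes the two Primary Series cohorts unlike. Both SAPs say they prevail over the protocol where methods differ, and both declare no changes from planned analyses, so nothing elsewhere resolves it.

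The direction (more omitted on vaccine) is a reasonable expectation from 2.3.3, not a documented fact. The size cannot be determined from the documents. On assumed rates it is negligible if such visits are rare (ratio shift under 0.01) and visible only near 1% of vaccinees (ratio about 1.08 to 1.15). A claim of material bias in the Part A safety conclusion would go beyond the evidence.

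Protocol 8.2.4 also calls clinically significant findings at study visits MAAEs, although 8.3.2 requires an unscheduled visit. That is a separate inconsistency, and this conclusion does not depend on it.

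**What to change.** 1. Define the MAAE and discontinuation rows to include solicited reactions recorded on the AE eCRF under 8.3.5, or keep the unsolicited rows and add a separate row for these events by arm or cohort. Include the treatment-related counterparts.
2. Apply the rule first to the Primary Series safety tables in SAP Part B/C 5.4.1.1 and 5.4.1.2, where the cohorts must be counted alike.
3. State the content of the Overall Stage MAAE and discontinuation tables explicitly, and align SAP Part A 6.6.1.1 and 6.6.1.2 with protocol Table 12.
4. For Part A, provide a supplementary tabulation by arm. SAP Part B/C Section 1 treats the Part A analyses as complete, with a CSR dated 03 August 2021, so rewriting those rows would be retrospective.

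The cost is SAP wording and some table programming. No new data collection is needed, because 8.3.5 already requires the records. The downside is that vaccine-arm MAAE counts become slightly less favourable.
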